Although center-based rehabilitation programs have proven benefit in terms of morbidity and mortality, they are underutilized and limited by lack of participation. A promising alternative to center-based programs is home-based programs. In these programs, patients do not need to leave their homes to exercise. Center personnel can provide indirect supervision, coaching, troubleshooting, and motivational interviewing via phone. One of the most widely available, standardized home-based programs currently available in the United States is home-based CR. Recent studies have demonstrated that home-based CR can be as beneficial as center-based CR and associated with better adherence and participation rates (Thomas RJ et al. Circulation 2019). The exercise component of CR is very similar to that of PR. Both programs are accredited by the American Association of Cardiovascular and Pulmonary Rehabilitation (AACVPR) and involve aerobic conditioning, strength training, and flexibility training. Thus, home-based CR may be a safe and viable option for patients with chronic kidney disease unable to attend a center-based program. The aim of our current study is to determine whether home-based CR will improve frailty parameters and SPPB scores in patients with varying levels of kidney function. If our hypothesis is supported by the findings of this study, a home-based exercise program could be implemented prior to kidney transplantation with the ultimate goal of improving HRQOL and transplant outcomes in kidney transplant candidates.

Purpose and Objectives

The purpose of our current study is to determine whether home-based cardiac rehabilitation is an effective intervention that will improve frailty parameters and Short Physical Performance Battery scores in patients with varying levels of kidney function. We will also determine if home-based exercise improves health-related quality of life, physical activity, and adverse outcomes, including hospitalizations and death. If our hypothesis is supported by the findings of this study, a home-based exercise program could be implemented prior to kidney transplantation with the ultimate goal of improving health-related quality of life and transplant outcomes in kidney transplant candidates in the future.

Protocol Risks/Subjects

Risk Category

Category 1: Research not involving greater than minimum risk.

Subjects

Gender:

Both

Age:

Adult (18-64 yrs), Geriatric (65+ yrs)

Ethnicity:

All Ethnicities

Primary Language:

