English

Groups to be recruited will include:

Patients

Which if any of the following vulnerable populations will be recruited as subjects?

Vulnerable populations require special protections. How will you obtain informed consent, protect subject confidentiality, and prevent undue coercion?

Pregnant woman/fetus

Will pregnant women and/or fetuses (as described in 45 CFR 46 Subpart B) be enrolled in the research?

No

Neonates

Will neonates of uncertain viability or nonviable neonates (as described in 45 CFR 46 Subpart B) be enrolled in the research?

No

Children

Will children be enrolled in the research?

No

Design/Procedure**Design**

Select one category that most adequately describes your research:

c) Pilot

Discuss the research design including but not limited to such issues as: probability of group assignment, potential for subject to be randomized to placebo group, use of control subjects, etc.

This study is a prospective interventional study, which involves use of existing and prospectively collected data. This pilot study will be conducted at Baylor College of Medicine examining the feasibility, safety, acceptability, and preliminary efficacy of home-based exercise on frailty parameters and Short Physical Performance Battery score in patients with varying levels of kidney function. We plan to accrue up to 20 adult patients with chronic kidney disease. The effects of exercise on health-related quality of life, physical activity, and adverse outcomes including hospitalizations and death, will also be explored.

Inclusion Criteria:

1. Age 18 years or older
2. Ability to consent to research
3. Chronic kidney disease (stages 1-5)
4. A Short Physical Performance Battery score ≤ 10 and/or considered frail or pre-frail according to the Fried Frailty Phenotype

Exclusion Criteria:

1. Younger than 18 years
2. Patients being evaluated for combined organ transplantation
3. Significant comorbidities that limit rehabilitation potential including pulmonary disease requiring continuous oxygen supplementation, active angina, critical aortic sclerosis, decompensated heart failure, or known ventricular arrhythmia.
4. An Short Physical Performance Battery score >10 or not considered frail or pre-frail by the Fried Frailty Phenotype
5. Non-English speaker without availability of adequate interpreter services (safety concern)
6. Failure to pass submaximal exercise test in patients not approved for kidney transplantation at our center

Procedure

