Screening and Recruitment:

Potential participants will be identified from dialysis units, nephrology clinics, primary care clinics, or kidney transplant clinics at Baylor College of Medicine clinic. If the study team is unable to reach the patient after three attempts involving phone calls and/or portal messages, an Institutional Review Board-approved contact letter may be sent up to two times. Patients who express interest in the study will go through the informed consent process with a member of the study team, and patients wishing to participate in the study will complete written consent. If patients have not had frailty and Short Physical Performance Battery testing within the two weeks prior to consent, the study team member will perform frailty and Short Physical Performance Battery testing at baseline in a supervised setting. Patients who are not frail or pre-frail and have a Short Physical Performance Battery score > 10 will be ineligible for study participation. Patients with stage 1-5 chronic kidney disease who are not currently approved for kidney transplant at our center will undergo a submaximal exercise test to rule out any significant, undiagnosed cardiopulmonary disease if they meet one or more of the following criteria: 1) diabetes, 2) age > 59, 3) prior coronary artery disease defined as history of myocardial infarction, coronary artery stenting, or coronary artery bypass grafting, or 4) current smoking. During the initial study visit, consenting patients will be provided with a pedal exerciser, resistance bands, and exercise pamphlets (Mayo Clinic Patient Education Pulmonary Rehabilitation: Exercise Program, Exercise Program Guidelines, Exercises for the Legs). Participants will be given the option of having the pedal exerciser mailed to their home.

Exercise Intervention:

Participants will be asked to complete an 8-week home-based exercise program with a focus on the core components of physical activity counseling and exercise training according to guidelines from the American Heart Association and the American Association of Cardiovascular and Pulmonary Rehabilitation (Balady GJ Circulation 2007). During the program, participants will receive weekly semi-scripted phone calls from an exercise physiologist from the Mayo Clinic Cardiac Rehabilitation program. During the baseline phone call, the exercise physiologist will assess the patients current level of physical activity; discuss warm-up, cool-

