A Data Transfer Agreement will be obtained between Mayo Clinic and Baylor College of Medicine so that a limited data set involving subjects from Mayo Clinic can be accessed from Baylor College of Medicine. Mayo Clinic will share the data with Baylor using encrypted email and/or Microsoft Simple Share. The limited dataset that will be shared will include demographics, dates of participation in the exercise intervention, information about the exercise intervention (i.e. duration of study phone calls, participant exercise log), study outcome data (including data from frailty assessments, body composition assessments, accelerometers, and questionnaires), and medical/laboratory information abstracted from the medical record.

Sample Size/Data Analysis

Sample Size

How many subjects (or specimens, or charts) will be used in this study?

Local: 20 Worldwide: 20

Please indicate why you chose the sample size proposed:

This is a pilot study so it doesn't require sample size calculations. However, we chose our recruitment target based on a prior study examining the impact of exercise on frailty parameters which was able to show significant differences with a similar number of study participants.

Data Analysis

Provide a description of your plan for data analysis. State the types of comparisons you plan (e.g. comparison of means, comparison of proportions, regressions, analysis of variance). Which is the PRIMARY comparison/analysis? How will the analyses proposed relate to the primary purposes of your study?

Categorical variables will be summarized as counts and percentages with continuous variables summarized via medians and interquartile ranges. Pre- and post- comparisons will be made using paired, one-sample Wilcoxon signed rank tests for continuous variables and chi-square tests for categorical variables. Differences between groups will be assessed using two-sample Wilcoxon tests for continuous variables and Fisher's exact tests for categorical variables. P-values less than 0.05 will be considered statistically significant. We will make no adjustments in the p-value for multiple hypothesis testing.

Potential Risks/Discomforts

Describe and assess any potential risks/discomforts; (physical, psychological, social, legal, or other) and assess the likelihood and seriousness of such risks:

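### Do the planned between-group tests in this pilot of at most 20 patients need to give way to a single trend test across CKD stages?

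*Combined protocol and SAP*

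**What the plan says.** The Design section describes a pilot: "We plan to accrue up to 20 adult patients with chronic kidney disease". The Sample Size section gives the same count, "Local: 20 Worldwide: 20". It makes no power calculation and refers instead to a "prior study examining the impact of exercise on frailty parameters which was able to show significant differences with a similar number of study participants". All participants are offered one intervention: under Exercise Intervention, "Participants will be asked to complete an 8-week home-based exercise program". No control arm or randomisation is described. Patients at any of the five CKD stages may enter.

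The Data Analysis section plans paired pre/post comparisons and then adds: "Differences between groups will be assessed using two-sample Wilcoxon tests for continuous variables and Fisher's exact tests for categorical variables". The decision rule is "P-values less than 0.05 will be considered statistically significant. We will make no adjustments in the p-value for multiple hypothesis testing". The section does not say what the groups are, which outcomes are compared between them, or how the Mayo Clinic data set enters the analysis. The aim in Background Information is to learn "whether home-based CR will improve frailty parameters and SPPB scores in patients with varying levels of kidney function".

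**The concern.** With no control arm, the groups would seem to be subgroups of at most 20 patients, so 10 v 10 is the best split. The size was justified by a study of the effect of exercise, not of a difference between kinds of patient.

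The title and aim mention kidney function, which suggests CKD stage as the grouping. A two-sample Wilcoxon test would then need the five stages cut in two. There are four possible cuts, and any cut discards the order.

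Two misreadings are at stake. A null result could be taken to show that the program works equally well at all levels of kidney function. A significant result from so small a sample would tend to overstate the difference. One rank trend test over the five stages looks like a cheap improvement.

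**Working it through.** **Inputs from the documents.** N is at most 20 and the significance level is 0.05 (taken as two-sided). No effect size, SD, group split or power is given, so there is no figure to reproduce. All effect sizes, splits and stage mixes below are assumptions.

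**1. Two-sample Wilcoxon, exact test, simulated normal data.** Where repeated runs differed by a point or two, the range is shown.

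| Split | 0.5 SD | 0.8 SD | 1.0 SD | 1.4 SD |
|---|---|---|---|---|
| 10 v 10 | 15–17% | 34–36% | 51–52% | 79–80% |
| 15 v 5 | 13% | 26–27% | 39% | 68% |

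Patients per group for 80% power, by the normal approximation n = 2(1.96 + 0.84)²/d²:
- d = 0.8: 2 × 7.85/0.64 = 24.5, so 25.
- d = 0.5: 2 × 7.85/0.25 = 62.8, so 63.

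Significant results at a true 0.5 SD average about 1.1 to 1.3 SD, more than twice the truth. So the tests miss most differences up to 0.8 SD, but at 10 v 10 they detect about half at 1.0 SD and four in five at 1.4 SD.

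**2. Fisher's exact test, 10 v 10.**
- 5/10 v 0/10: p = 2 × C(10,5)/C(20,5) = 504/15504 = 0.033.
- 4/10 v 0/10: p = 2 × C(10,4)/C(20,4) = 420/4845 = 0.087.

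Enumeration of all tables puts the smallest significant gap at 50 points. Power for 60% v 20% is 25%.

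**3. Error rate.** With no true effect, each single Wilcoxon cut rejects 4% to 5% of the time, and Fisher's test 0.8% to 2.5%. The rate rises to 8% to 15% only if several cuts are tried and the best is kept, which the plan does not propose.

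**4. Trend test against a cut.** Five assumed stage mixes (stages 1 to 5): 4/4/4/4/4, 2/3/5/5/5, 1/2/4/5/8, 0/2/4/4/10 and 0/0/5/5/10.

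- *Correlation 0.5 between stage and change in every mix:* the rank trend test has 62% to 66% power and the best single cut 46% to 54%.
- *What that assumes:* the slope per stage, in residual SDs, is r/√(1 − r²) divided by the SD of stage. With r = 0.5 the numerator is 0.577. The even mix has a stage SD of 1.414, so the slope is 0.577/1.414 = 0.41, a stage 1-to-5 shift of 4 × 0.41 = 1.6 SD. The mix 0/0/5/5/10 has a stage SD of 0.829, so the slope is 0.577/0.829 = 0.70. Fixing the correlation therefore raises the assumed effect per stage as the mix narrows.
- *Slope held at 0.41 SD per stage:* trend power over the five mixes is 65%, 56%, 48%, 40% and 28%. The best cut gives 49%, 40%, 38%, 30% and 22%.
- *Correlation 0.3:* trend about 24% to 26%, best cut about 18% to 19%.
- *Only stage 5 differs, even mix:* at 1.0 SD, trend 17% to 18% v 37% for the cut at stage 5; at 1.5 SD, 31% v 68%.

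**5. Is CKD stage the grouping?** Background Information, Purpose and Objectives, and Design all ask whether exercise helps patients whose kidney function varies. Read plainly, that describes who is enrolled. No objective asks whether benefit differs by stage. The plan also records dialysis details and mentions a Mayo Clinic data set. Dialysis v no dialysis, or Mayo v Baylor, gives two groups with no stage cut. If Mayo patients were a separate cohort of 10 to 30 (assumed), the difference detectable with 80% power by a t-test would be 1.12 to 0.83 SD, against 1.32 SD at 10 v 10.

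**The case for a change.** The best case for a change is that it costs a few sentences and no new data, since CKD stage is known at entry. Low power holds for any split of the 20 patients. The trend test beats the best cut in the steady-trend scenarios above. A pilot is better served by estimates with confidence intervals than by unadjusted tests of unnamed groups. The form also asks which comparison is primary, and the answer names none.

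Much of this stands. The power figures reproduce, the grouping is undefined, and a non-significant result here would not show equal benefit.

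Three parts do not carry the change. First, saying that the tests miss most real differences needs an effect size; it is true up to 0.8 SD and not at 1.4 SD. Second, only the Wilcoxon test needs the stages cut in two: Fisher's test extends to a five-row table, though it ignores order. Third, the suggested remedy would make SPPB change the sole primary comparison although frailty parameters and SPPB are named together, drop p-values for other group comparisons, and bar pooling of Mayo patients. Statisticians could reasonably differ on each, and the last could remove the comparison that was intended.

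**Conclusion.** No change is called for. If the groups are subgroups of the 20, power is about 36% or less for differences up to 0.8 SD, and Fisher's test at 10 v 10 needs a gap of at least 50 points. Those are limits of a declared pilot that promises no power for these comparisons. They are not an error in a stated figure or rule, and the tests keep their level. The paired pre/post analysis is untouched by this point.

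What remains is an undefined word. The report has to say which groups were compared, and a careful analyst will present such comparisons as exploratory and not read a null as equivalence. A trend test over CKD stage is one reasonable option if stage proves to be the grouping: somewhat stronger for a steady trend, weaker if only stage 5 differs, and still below 50% power in many plausible mixes. This conclusion rests on assumed effect sizes, splits and stage mixes, and on reading the aim's reference to kidney function as a description of the population.
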